4. HYPOTHESES AND DECISION RULES

4.1. Statistical Hypotheses

For the Expansion Cohort of LDAC combination for efficacy (Unfit Patients), a total of 15 patients will provide 80.8% power to reject the null hypothesis DMR rate=6.8% when the true DMR rate=34.1% for the alternative hypothesis. The DMR rates for the hypotheses are based on the result of the analysis based on the derived response for B1371003 CSR (P2 Unfit, data cut off: 3 Jan 2017).

For other cohorts, there are no formal statistical hypotheses. The emphasis of the primary analysis will be on estimation of key summary statistics.

4.2. Statistical Decision Rules

For cohorts excluding the Expansion Cohort of LDAC combination for efficacy (Unfit Patients), *no statistical sample size determination was performed. The number of patients to be enrolled in the study depends on the observed safety profile within the cohorts. The total expected number of patients is estimated to be 34 patients.* For Expansion Cohort of LDAC combination for efficacy (Unfit Patients), the statistical decision rule is described as follows.

Monotherapy Cohort:

The DLT evaluation period includes the PK lead-in period, and the first cycle of treatment. Dose escalation to the 100 mg QD dose level will occur if <1/3 or <2/6 patients at the 50 mg QD dose level experience DLT during the first cycle of treatment. If ≤1 patient experiences a DLT event in the first 3 patients, an additional 3 patients will be enrolled to give a total of 6 patients in the 100 mg QD cohort. If ≤1 of the 6 patients experiences a DLT by the end of Cycle 1, the tolerability of the 100 mg QD dose level in the monotherapy cohort will be deemed confirmed, and the study will proceed to the combination cohort. If 2 or more of the 6 patients treated at 100 mg QD in the monotherapy cohort experience a DLT by the end of Cycle 1, an intermediate dose level (80 mg QD) may be explored in the monotherapy cohort prior to proceeding with the combination cohort. If two or more of the 3 or 6 patients treated at 50 mg QD in the monotherapy cohort experiences a DLT by the end of Cycle 1, the dose escalation will be terminated, and a lower dose may be explored.

Combination Cohorts:

Combination Cohort 1 (Unfit Patients):

A total of 6 patients will be treated in this cohort and followed up for DLT evaluation. The DLT evaluation period includes the first cycle of treatment. If ≤ 1 of the 6 patients experiences a DLT by the end of Cycle 1, the tolerability of the combination will be deemed confirmed. If more than 2 of the 6 patients experience a DLT by the end of Cycle 1, additional lower dose levels may be tested, applying identical criteria to those outlined above with respect to DLT events.

Expansion Cohort of LDAC Combination for Efficacy (Unfit Patients):

The combination of PF-04449913 and LDAC will be considered superior to the historical data of LDAC as single-agent with respect to DMR if the DMR rate is statistically significant at the 1-sided 0.05 level using exact test for a single proportion. An observed DMR rate of 26.7% or above (eg, 4 or more responders out of 15 patients) will reject the null hypothesis.

Combination Cohort 2 (Fit Patients):

A total of 6 patients will be treated in this cohort and followed up for DLT evaluation. If ≤ 1 of the 6 patients experiences a DLT event by the end of Induction Cycle 1, the tolerability of the combination will be confirmed. If more than 2 of the 6 patients experience a DLT by the end of Induction Cycle 1, additional lower dose levels may be tested using identical criteria to those outlined above with respect to DLT events.

Combination Cohort 3 (Azacitidine Combination):

A total of 6 patients will be treated in this cohort and followed up for DLT evaluation. The DLT evaluation period includes the first cycle of treatment. If ≤ 1 of the 6 patients experiences a DLT by the end of Cycle 1, the tolerability of the combination will be deemed confirmed. If more than 2 of the 6 patients experience a DLT by the end of Cycle 1, the investigator and the sponsor will review all available safety data and discuss the next steps.

Continuation Cohort:

No decision rule for this cohort.

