As of 7 August 2014, it was decided by the study team that a lower dose level (25 mg QD) will be explored in the study, since evaluation of PD data at the 25 mg QD dose is scientifically warranted. Up to 3 patients will be enrolled at the 25 mg dose level. DLT evaluation will be performed on this dose level, however, it will not be used for the dose escalation decision, or for the determination of whether or not to proceed with the combination cohort. The Sponsor will discuss with the Investigator to confirm that there is no safety issue for patients enrolled at this dose level.

Treatment with PF-04449913 may continue for up to 12 cycles or until disease progression or relapse, patient withdrawal, or unacceptable toxicity occurs (whichever is first). Patients who complete 12 cycles of treatment will be deemed to have completed the study. However, patients who complete 12 cycles of study treatment who demonstrate clinical benefit with manageable toxicity, and are willing to continue receiving the study treatment, may be given the opportunity to do so following agreement between the Investigator and Sponsor, and

pending study drug availability. If treatment continues beyond 12 cycles, study procedures should continue to be performed as per [Table 1](#) (See Schedule of Activities).

The study may at any time evaluate additional dose levels of single-agent PF-04449913 based upon the emerging data from the ongoing pre-clinical and clinical studies, following discussion between the Investigators and the Sponsor.

Combination Cohorts:

The combination cohorts will evaluate the safety and tolerability of PF-04449913 at the starting dose of 100 mg once daily continuously administered in combination with 3 different chemotherapy regimens.

Combination Cohort 1 (Unfit Patients):

In this cohort, patients who are “unfit for intensive chemotherapy” based on predefined criteria (See Inclusion Criteria) will receive PF-04449913 once daily continuously in combination with LDAC over 28 day cycles.

A total of 6 patients will be treated in this cohort and followed up for DLT evaluation. The DLT evaluation period includes the first cycle of treatment. If ≤ 1 of the 6 patients experiences a DLT by the end of Cycle 1, the tolerability of the combination will be deemed confirmed. If 2 or more of the 6 patients experience a DLT by the end of Cycle 1, additional lower dose levels may be tested, applying identical criteria to those outlined above with respect to DLT events.

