A total of 6 patients will be treated in this cohort and followed up for DLT evaluation. If ≤ 1 of the 6 patients experiences a DLT event by the end of Induction Cycle 1, the tolerability of the combination will be confirmed. If 2 or more of the 6 patients experience a DLT by the end of Induction Cycle 1, additional lower dose levels may be tested using identical criteria to those outlined above with respect to DLT events.

Treatment will continue until disease progression or relapse, patient refusal, or unacceptable toxicity (whichever is first). Fit patients who complete induction, consolidation and 6 cycles of maintenance with PF-04449913 will be deemed to have completed the study treatment. However, patients who complete the 6 cycles of maintenance and demonstrate clinical benefit with manageable toxicity, and are willing to continue receiving single-agent PF-04449913, may be given the opportunity to do so following agreement between the Investigator and Sponsor, and pending study drug availability. If treatment continues beyond the 6 cycles of maintenance, study procedures should continue to be performed as listed in Table 3 (Schedule of Activities).

Combination Cohort 3 (Azacitidine Combination):

In this cohort, patients with previously untreated AML and eligible for non-intensive chemotherapy will receive PF-04449913 once daily continuously at the starting dose of 100 mg in combination with azacitidine over 28 day cycles.

A total of 6 patients will be treated in this cohort and followed up for DLT evaluation. The DLT evaluation period includes the first cycle of treatment. If ≤ 1 of the 6 patients experiences a DLT by the end of Cycle 1, the tolerability of the combination will be deemed confirmed. If 2 or more of the 6 patients experience a DLT by the end of Cycle 1, the investigator and the sponsor will review all available safety data and discuss the next steps.

Since responses to azacitidine may require 4-6 cycles of administration to emerge, treatment with the study drug combination should be continued for at least 6 cycles, or until death, unacceptable toxicity, or patient refusal (whichever is first). If documentation of disease progression occurs within the first 6 cycles of study treatment, the patient **SHOULD NOT** be

withdrawn from study treatment following agreement between the Investigator and Sponsor if, in the Investigator's judgment, the patient is still likely to receive clinical benefit.

[figure not shown]

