9.6. Data Safety Monitoring Committee

An external Data Safety Monitoring Committee will not be established for the study. For the purpose of this protocol, Pfizer procedures for periodic safety review will be applied by an internal safety review team with medical and statistical capabilities to review individual and summary data collected in the safety and clinical databases.

Procedures include:

- Surveillance for serious adverse events (SAEs) according to regulatory guidelines;
- Discussions between the Investigators and the Sponsor of AEs and laboratory tests alterations seen at each cohort in an on-going manner at regular teleconferences and/or meetings to determine the safety profile and risk/benefit ratio and decide if further enrollment is appropriate.

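### SAP 4.2 gives no next step for exactly 2 DLTs in 6 patients in Combination Cohorts 1, 2 and 3, and its threshold differs from the protocol's

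*SAP*

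**What the plan says.** SAP 4.2 sets a two-part rule for each six-patient combination cohort. The first part is the same throughout: at most 1 DLT in 6 confirms tolerability. The second part states when something further happens:

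- Combination Cohort 1: "If more than 2 of the 6 patients experience a DLT by the end of Cycle 1, additional lower dose levels may be tested".
- Combination Cohort 2: "If more than 2 of the 6 patients experience a DLT by the end of Induction Cycle 1", again leading to possible testing of lower doses.
- Combination Cohort 3: "If more than 2 of the 6 patients experience a DLT by the end of Cycle 1, the investigator and the sponsor" review the safety data and discuss what to do next.

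The protocol has the same first part but a different second part, both in the Protocol Summary and in Section 3.1.2:

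- Cohort 1: "If 2 or more of the 6 patients experience a DLT by the end of Cycle 1, additional lower dose levels may be tested".
- Cohort 2: "If 2 or more of the 6 patients experience a DLT by the end of Induction Cycle 1".
- Cohort 3: "If 2 or more of the 6 patients experience a DLT by the end of Cycle 1, the investigator and the sponsor".

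For 100 mg monotherapy, SAP 4.2 itself uses the protocol's form: "If 2 or more of the 6 patients treated at 100 mg QD in the monotherapy cohort experience a DLT".

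**The concern.** With confirmation at 0 or 1 and action only from 3, a cohort with exactly 2 DLTs falls between the two branches. A reader working from the SAP finds no instruction for that result, and a reader holding both documents finds two different triggers.

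First-cycle DLTs head the primary endpoint in these three cohorts (Protocol 2.2), and SAP 4.2 is the section that sets out the decision rules, so the threshold there should be complete and should agree with the protocol. Two further points follow:

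- In Cohorts 1 and 2, any lower dose would be judged by the same criteria, so the gap could carry over to that dose.
- SAP Section 2 requires departures from the SAP to be described in the study report. A team that followed the protocol at 2 of 6 would be acting outside the SAP's stated trigger.

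**Working it through.** **Step 1. List every outcome.** Each cohort has 6 patients evaluated for DLT (SAP 4.2; Protocol 3.1.2).

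| DLTs in 6 | Protocol 3.1.2 | SAP 4.2 |
|---|---|---|
| 0–1 | confirmed | confirmed |
| 2 | action | no branch |
| 3–6 | action | action |

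The protocol's branches cover all seven counts; the SAP's cover six of them.

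**Step 2. Look for an intended change.** The SAP's table of amendments (Section 1) lists no change to a DLT threshold. Even a deliberate move to 3 or more would need a branch for 2.

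**Step 3. How often the omitted count would arise.** The documents state no operating characteristic for this rule, so there is no figure to reproduce, and they assume no DLT rate, so p below is an assumption. With X ~ Binomial(6, p):

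- P(X = 2) = 15 p²(1 − p)⁴
- P(X ≤ 1) = (1 − p)⁶ + 6p(1 − p)⁵

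For example, at p = 0.10, P(X = 2) = 15 × 0.01 × 0.6561 = 0.0984 and P(X ≤ 1) = 0.5314 + 0.3543 = 0.8857.

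| p | P(X ≤ 1), confirmed | P(X = 2), omitted | P(X ≥ 2), protocol trigger | P(X ≥ 3), SAP trigger | P(X = 2) / P(X ≥ 2) |
|---|---|---|---|---|---|
| 1/16 | 0.9505 | 0.0453 | 0.0495 | 0.0042 | 0.915 |
| 0.10 | 0.8857 | 0.0984 | 0.1143 | 0.0159 | 0.861 |
| 0.20 | 0.6554 | 0.2458 | 0.3446 | 0.0989 | 0.713 |
| 1/3 | 0.3512 | 0.3292 | 0.6488 | 0.3196 | 0.507 |

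The last column is the share of cohorts failing the confirmation rule that land on exactly 2.

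**Step 4. Which p is plausible.** Protocol 1.2.8.1.3 reports, at a 100 mg starting dose, no DLT among 17 patients on the LDAC combination and one among 16 on the intensive-chemotherapy combination. These are treated patients; the DLT-evaluable numbers are not given. Both point to the low end of the table. The samples are small: the two-sided 95% Clopper–Pearson upper limits are 19.5% (0/17) and 30.2% (1/16), and at those rates P(X = 2) is 24.0% and 32.5%.

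**The case against.** The strongest reply is that this is a slip in a secondary restatement and that no decision turns on it. Most of that stands:

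- The confirmation rule is identical in both documents, so the chance of declaring a regimen tolerable is unchanged. Neither document calls 2 of 6 tolerable.
- The protocol's rule sits in its design section (3.1.2). SAP Section 1 supersedes only the protocol's statistical sections, and SAP Section 2 describes the SAP as a supplement to the protocol. The protocol's rule therefore still guides conduct.
- The action is optional in Cohorts 1 and 2 and a review in Cohort 3, and the SAP forbids neither at 2 of 6. Protocol 9.6 also provides for "Discussions between the Investigators and the Sponsor of AEs and laboratory tests alterations seen at each cohort in an on-going manner".
- SAP 8.2.1 only tabulates and lists DLTs, and SAP 4.1 sets no formal hypothesis for these cohorts.
- Protocol 1.2.8 gives 45 patients enrolled and treated as of 29 January 2020, out of at most 49, so the DLT decisions had probably largely been made. That is an inference.

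It is also fair to say that SAP v4 was based on protocol amendment 7, whereas the supplied protocol refers to amendment 8. Whether the SAP matched its own base text cannot be checked, and the cause of the mismatch cannot be established.

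What does not stand is the idea that the SAP can be left as it is. The missing branch is visible within the SAP alone, whichever protocol version applies, and the SAP's monotherapy rule shows the form that closes it.

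**Conclusion.** The point holds. In all three combination cohorts the trigger stated in SAP 4.2 leaves 2 of 6 unaddressed and disagrees with the supplied protocol. This conclusion rests on the wording alone and needs no assumption. How often the omitted count would arise does depend on an assumed DLT rate: about 4.5% per cohort at 1 in 16, rising to about 33% at one third, with earlier 100 mg data favouring the low end. The practical consequence is small, but this is a wrong threshold in the section that states the decision rules, and it should be corrected.

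**What to change.** In the three SAP 4.2 sentences for Combination Cohorts 1, 2 and 3, change the threshold from more than 2 to 2 or more of the 6 patients. The branches then become 0–1 (confirmed) and 2–6 (action), which cover every outcome and match Protocol 3.1.2. The cost is three wording corrections in the SAP; the design, sample size, tables and analyses stay as they are.

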5. ANALYSIS SETS

Analysis sets are defined as below although the patients enrolled in the Expansion Cohort of LDAC combination for efficacy (Unfit Patients) are excluded from DLT-evaluable analysis set and the patient enrolled in the Continuation Cohort is excluded from all of these analysis sets except the safety analysis set. The patient enrolled in the Continuation Cohort is included in the safety analysis set if the patient receives at least one dose of study medication.

5.1. Full Analysis Set

The full analysis set includes all enrolled patients who receive at least one dose of study medication on or after Cycle 1/Day 1 (Induction Cycle/Day 1 for fit patients in the Combination Cohort 2).

5.2. DLT-evaluable Analysis Set ('Per Protocol' Analysis Set)

The per protocol analysis set includes all enrolled patients who receive at least one dose of study medication and who do not have major treatment deviations during first cycle (DLT observation period). Patients with major treatment deviations during the DLT observation period are not evaluable for the DLT assessment and will be replaced as needed. Major deviations include, but are not limited to, administration of less than 80% of the planned dose during the DLT observation period of PF-04449913 or any component of the combination therapy [LDAC for Combination Cohort 1 (Unfit Patients), cytarabine/daunorubicin for Combination Cohort 2 (Fit Patients), and azacitidine for Combination Cohort 3 (Azacitidine Combination)] for reasons other than drug related toxicity.

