Patients who receive less than 80% of the planned dose of any of the study drugs in the first cycle of treatment for reasons other than treatment-related toxicities are not evaluable for DLT, and should be replaced to adequately assess the safety of study treatments. At the time of dose escalation and when proceeding to the next cohort, Sponsor will discuss with Investigator to confirm there is no safety issue of patients who are not evaluable for DLT and replaced.

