9.1. Analysis Sets

In this study, analysis sets are defined as below although the patients enrolled in the Expansion Cohort of LDAC combination for efficacy are excluded from DLT-evaluable analysis set and the patient enrolled in the Continuation Cohort is excluded from all of these analysis sets except the safety analysis set. The patient enrolled in the Continuation Cohort is included in the safety analysis set if the patient receives at least one dose of study medication.

1. Safety analysis set:

The safety analysis set includes all enrolled patients who receive at least one dose of study medication.

2. Full analysis set:

The full analysis set includes all enrolled patients who receive at least one dose of study medication on or after Cycle 1/Day 1 (Induction Cycle/Day 1 for fit patients in the Combination Cohort 2).

3. DLT-evaluable analysis set:

The per protocol analysis set includes all enrolled patients who receive at least one dose of study medication and who do not have major treatment deviations during first cycle (DLT observation period). Patients with major treatment deviations during the DLT observation period are not evaluable for the DLT assessment and will be replaced as needed. Major deviations include, but are not limited to, administration of less than 80% of the planned dose during the DLT observation period of PF-04449913 or any component of the combination therapy [LDAC for Combination Cohort 1 (Unfit Patients), cytarabine/daunorubicin for Combination Cohort 2 (Fit Patients), and azacitidine for Combination Cohort 3 (Azacitidine Combination)] for reasons other than drug related toxicity.

4. PK analysis sets:

The PK concentration population is defined as all treated patients who have at least 1 concentration of any of the study drugs. The PK parameter analysis population is defined as all treated patients who have at least one of the PK parameters of interest of any of the study drugs.

5. QTc-evaluable analysis set:

The QTc-evaluable dataset is defined as all patients who have baseline and at least one triplicate ECG assessment after having at least one PF-04449913 dose on study.

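### The DLT-evaluable definition has no clause keeping a patient who has already had a DLT, so an observed DLT can leave the count behind the 1-of-6 tolerability rule

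*SAP*

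**What the plan says.** Evaluability for the DLT endpoint is defined in three places.

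- **SAP 5.2**, repeated in Protocol 9.1: "Patients with major treatment deviations during the DLT observation period are not evaluable for the DLT assessment and will be replaced as needed". The dose criterion is "administration of less than 80% of the planned dose during the DLT observation period of PF-04449913 or any component of the combination therapy", limited to shortfalls arising "for reasons other than drug related toxicity". The list of deviations is open: "Major deviations include, but are not limited to".
- **Protocol 3.2, Patient replacement**: the rule covers "Patients who receive less than 80% of the planned dose of any of the study drugs in the first cycle". It is confined to shortfalls with a non-toxicity cause, and it has these patients classed as non-evaluable and replaced. At dose escalation, and before moving to the next cohort, the sponsor discusses with the investigator to "confirm there is no safety issue of patients who are not evaluable for DLT and replaced".
- **SAP 8.2.1**: the primary DLT tables for the Monotherapy Cohort and Combination Cohorts 1 to 3 use the DLT-evaluable set. The accompanying listing covers every record on the DLT case report form page.

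The decision itself is in Protocol 3.1.1 and 3.1.2 and SAP 4.2. Tolerability at 100 mg, alone or in combination, is confirmed when at most 1 of 6 patients has a DLT. At 50 mg monotherapy, escalation needs fewer than 1 of 3 or fewer than 2 of 6.

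**The concern.** Evaluability turns on the fraction of dose received, the reason for any shortfall, and an open list of other deviations. Whether the patient has already had a DLT plays no part. Consider a patient with a related DLT who later stops because of progression or withdrawn consent and so falls below 80% of planned dose. Read literally, all three sections make this patient non-evaluable and call for a replacement.

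First-cycle DLT heads the primary endpoint in four cohorts, and with six patients a single event decides the outcome. A patient who has had a DLT has already supplied the information that the rule needs. Incomplete dosing makes the absence of a DLT uninformative, but not its presence. An 80% criterion is therefore sound for DLT-free patients and produces a wrong count when applied to the others.

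**Working it through.** **Direct case.** Seven patients are treated and two have a DLT. One of those two receives under 80% of a study drug for a non-toxicity reason.

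- As written, that patient is replaced and the count is 1 of 6: confirmed.
- With the patient kept, two DLTs are counted: not confirmed.

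**How easily the threshold is crossed.** Combination Cohort 1 plans 26 doses of PF-04449913 in Cycle 1 (Days 3 to 28). Missing six leaves 20/26 = 76.9%. Combination Cohort 3 plans 27 (Days 2 to 28), and missing six leaves 21/27 = 77.8%. On the short backbones, missing one of three daunorubicin days leaves 2/3 = 67%, and missing two of seven azacitidine days leaves 5/7 = 71%.

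**Operating characteristics.** The documents give none for this rule, so there is no figure to reproduce. Inputs:

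- *p*, true DLT rate: not given; 0.30 assumed, with 0.20 and 0.40 as a range.
- *q*, chance that a DLT-free patient is excluded: not given for this trial. Protocol 1.2.8.1.1 reports that 6 of 47 patients in B1371001 were not evaluable under a similar 80% rule, so *q* = 6/47 = 0.128. It does not say whether any of the six had a DLT, so using this as the DLT-free rate is an assumption.
- *d*, chance that a patient with a DLT is excluded: not given; 0.10, 0.20 and 0.30 assumed.

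Formulas, with six evaluable patients behaving independently:

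- DLT rate among evaluable patients as written: r = p(1−d) / [p(1−d) + (1−p)(1−q)]
- DLT rate if DLT patients are always kept: r = p / [p + (1−p)(1−q)]
- Chance of confirming: C(r) = (1−r)^6 + 6r(1−r)^5

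At p = 0.30, (1−p)(1−q) = 0.70 × 0.872 = 0.611.

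| Situation | r | C(r) |
|---|---|---|
| No exclusions | 0.300 | 0.42 |
| As written, d = 0.10 | 0.270/0.881 = 0.307 | 0.41 |
| As written, d = q = 0.128 | 0.300 | 0.42 |
| As written, d = 0.20 | 0.240/0.851 = 0.282 | 0.46 |
| As written, d = 0.30 | 0.210/0.821 = 0.256 | 0.52 |
| DLT patients always kept | 0.300/0.911 = 0.329 | 0.36 |

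The pattern is the same elsewhere in the range:

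- p = 0.20: 0.66 with no exclusions; 0.64, 0.69 and 0.74 as written for the three values of d; 0.60 with DLT patients kept.
- p = 0.40: 0.23 with no exclusions; 0.22, 0.27 and 0.32 as written; 0.19 with DLT patients kept.

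When d = q the formula returns r = p, so there is no average shift, although an individual DLT can still be dropped.

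**The case against.** The strongest reply is that the situation is rare and already watched.

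- **Toxicity shortfalls do not exclude.** After a related Grade 3 or higher non-haematologic event, PF-04449913 is generally withheld (Protocol Tables 13 and 19). The resulting shortfall is due to toxicity, so the patient stays evaluable. Under Protocol 3.2, failure to deliver 80% of doses because of non-haematologic toxicity is itself a DLT. In B1371001 both patients with a DLT had dosing interrupted and were reported among the 41 evaluable.
- **Little backbone remains to be missed after a first-week DLT.** Daunorubicin/cytarabine and azacitidine finish by Day 7 of Cycle 1. Missed LDAC or daunorubicin/cytarabine doses can be made up at the investigator's judgement (Protocol 5.3.9).
- **The event is not hidden.** It comes up in the discussion of replaced patients, in the DLT listing, and in the adverse-event tables, which use the Safety Analysis Set (SAP 8.2.4.1).
- **Much of this is probably past.** Protocol 1.2.8 records 45 patients treated by 29 January 2020, out of a maximum of 49.

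All of this stands, and it limits the weight of the point. It does not remove it. Progression, withdrawal or another deviation after a DLT still excludes the patient, and none of the safeguards returns the event to the count or to the primary table.

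A reader might also infer that the rule can only lower the DLT count and so always favours confirmation. The documents do not support that. The same 80% rule removes DLT-free patients, which raises the observed rate. Setting q = 0 would give 0.47, 0.52 and 0.58 at p = 0.30, but that assumes no DLT-free patient is ever excluded, contrary to the 6 of 47 in B1371001.

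**Conclusion.** The point holds as a defect in the definition. Following Protocol 3.2 and 9.1 and SAP 5.2 literally can remove an observed DLT from the decision and from the primary table, and one removal is enough to turn 2 of 6 into 1 of 6.

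Its average effect is modest and conditional. Relative to the true rate, the rule leans toward confirming only if non-toxicity exclusion is likelier after a DLT than without one. That is plausible, for instance if withdrawal after a toxic event is recorded as refusal, but nothing in the documents shows it. At a 30% true rate and 13% exclusion of DLT-free patients, the chance of confirming moves from 0.42 to between 0.41 and 0.52. Against a definition that keeps every DLT (0.36), the written rule is more permissive throughout that range. The values of p, q and d are all assumptions.

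The documents do not show that a DLT patient was in fact excluded or replaced, and that should not be inferred. The change is worth making because a few words prevent a wrong count; it is not a reason to set aside the tolerability conclusions.

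**What to change.** In Protocol 3.2 and 9.1 and SAP 5.2, state that any treated patient with a DLT in the observation period is DLT-evaluable, whatever fraction of dose was received and whatever other deviations occurred. The 80% rule, other major deviations and replacement then apply only to patients without a DLT. The 1-of-6 criterion, doses and clinical management are unchanged.

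For cohorts already completed, use the DLT listing to check whether any patient with a DLT was excluded or replaced, and report the answer beside the primary DLT table. If one was, show the count both ways.

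The cost is one sentence in each of three sections and a short check. The trade-off is a more conservative count. Keeping every DLT while replacing only DLT-free patients raises the effective rate from 0.30 to 0.33 under the assumptions above, and lowers the chance of confirming from 0.42 with no exclusions to 0.36. The sponsor should accept this knowingly.
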